Methods: This study is a large, simple and pragmatic trial that compares two protocols for CT surveillance of potentially cancerous small lung nodules. The two protocols are both supported by guidelines from professional societies and consistent with current standards of care. Random assignment to intervention groups will occur at the level of the hospital or health system, and clinical champions at each site will work with clinical and operational leaders to implement the assigned protocol for surveillance during the study period. Eligible patients will be enrolled passively at one of 24 hospitals within 14 health care systems, using automated methods for identification, notification, and registration into the study. We plan to enroll approximately 35,200 unique patients over 28 months and follow them for two years to ascertain outcomes. Data will be collected from electronic health records (EHRs), local and statewide cancer registries, and surveys of patient-reported and provider-reported outcomes. All data will be transferred securely to the Data Coordinating Center for analyses using hierarchical models to account for clustering effects and to adjust for residual imbalances between groups. Sensitivity analyses and analyses to identify heterogeneity of treatment effect will be performed.

Patient Outcomes: Based on our extensive clinical experience, engagement with stakeholders, and qualitative research with patients to date, we have identified the following set of clinical and patient-centered outcomes of interest. Most of the outcomes are amenable to collection by reviewing EHRs.

1. Tumor (T) stage >T1a at diagnosis, according to the American Joint Committee on Cancer (AJCC) classification system, 7th edition, equivalently, stage >T1b according to the AJCC 8th edition;
2. TNM stage >T1aN0M0, according to the American Joint Committee on Cancer (AJCC) classification system, 7th edition, equivalently, stage >T1bN0M0 according to the AJCC 8th edition;
3. Timeliness of lung cancer diagnosis;
4. Lung cancer survival, obtained from membership files and state tumor registries;
5. Emotional distress during surveillance period, measured with the Impact of Event Scale-Revised (IES-R);
6. Anxiety, measured with the 6-item State-Trait Anxiety Inventory (STAI-6);
7. General health status;
8. Overall satisfaction with evaluation;
9. Health care resource utilization during the surveillance period;

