Random assignment to one of the two intervention groups at the hospital or health system level will be performed using matching^{45,46} and re-randomization⁴⁷ to ensure balance among several potential confounders: the volume of CT imaging performed, the setting type (integrated healthcare system vs. academic), KPSC vs. other institutions; racial and ethnic distribution; percentage of patients who are current, former, vs. never smokers; inclusion of patients with screening-detected nodules; frequency in using PET for patients with nodules 11-15mm; timing of notification letters to participants; and distribution of insurance type. A biostatistician at the Data Coordinating Center will generate the allocation scheme using statistical software developed in R by [name] at Vanderbilt^{45,46}. All participating organizations have agreed to accept random assignment to one of the two groups. While many of the participating

institutions operate more than one hospital, all but one will undergo randomization at the health system level, because their information systems for managing radiology results are centralized, so assigning individual hospitals to different groups would be difficult. The one exception is KPSC, which operates hospitals in 11 distinct medical service areas (MSA); clinical and administrative leaders at this site have agreed to randomization at the level of the MSA. Site PIs, clinical champions, and their multidisciplinary collaborators (including radiologists, primary care physicians, pulmonologists, oncologists and surgeons) will work with key administrative leaders and other clinicians to implement the assigned imaging protocols during the study period. Although randomization is at the hospital level, the unit of analysis will be the individual patient, and we will compare patients randomized to more vs. less frequent surveillance, after adjusting for potential clustering within sites.

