Timeliness of treatment: To investigate whether among participants with cancerous nodules, less intensive surveillance will be non-inferior to more intensive surveillance for timeliness of treatment, we will restrict our analysis to participants with cancerous nodules and use Cox regression models where time from initial nodule identification to treatment is the outcome variable. Patients who die or do not receive treatment will be censored at end of follow-up. We will consider using competing risk models, as necessary.

H1c: Secondary endpoint

Survival: To investigate whether among participants with cancerous nodules, less intensive surveillance will be non-inferior to more intensive surveillance for overall survival, we will restrict our analysis to participants with cancerous nodules and use Cox regression models where time from initial nodule identification to death as the outcome variable. Patients will be censored at end of follow-up.

For all time-to-event analyses, clustering by site will be handled by specifying subjects nested within each cluster and using robust sandwich estimators for statistical inferences.⁶¹ The proportionality assumption will be checked by creating log-minus-log plots. To explore whether individuals who are most likely to benefit from more intensive surveillance, subgroup analyses will examine the effect of age (using the median and/or quartile values as cut points), nodule size (>8 mm), nodule attenuation (solid or part-solid nodules compared with non-solid nodules), and mode of detection (detected by screening compared with incidentally detected).

Analytically, we will include interaction terms between each of these factors with treatment in the models, respectively. For significant interactions, we will also conduct subgroup analysis to explore the treatment effects in corresponding subgroups. Since the study is not powered to test interaction terms, these analyses will be exploratory. For H1b, to study whether among participants with cancerous nodules, more intensive surveillance will result in more timely diagnosis and treatment than less intensive surveillance, we will adopt similar strategy used for comparing overall survival described above.

H2a:

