adherence indicators and the surveillance arm will be obtained. To examine whether among all participants with a lung nodule ≤ 15 mm, more intensive surveillance will be associated with worse adherence to the surveillance protocol than less intensive surveillance, we will use hierarchical logistic regression that includes random site effects, with and without adjusting for potential confounders including age, gender, ethnicity/race, smoking, BMI, nodule size, and any facility-level factors balanced during the randomization.

Sample size and power calculations by aim

Preliminary data from a retrospective study of patients who underwent one or more chest CT scans at KPSC (2006-2012) showed that 76% of chest CT scans are performed in unique patients, and that approximately 30% of these individuals will have a prior history of cancer. Of the remainder, approximately 32% of unique patients (with no prior cancer diagnosis) who undergo chest CT will have a pulmonary nodule ≤ 30 mm, and 72% of all nodules measure ≤ 15 mm. Thus, we expect that approximately 16% of all unique patients who undergo chest CT will have a qualifying pulmonary nodule measuring ≤ 15 mm and no prior history of cancer. Data provided by participating sites indicates that more than 376,000 chest CT scans will be performed during the planned 20-month enrollment period in over 279,500 unique individuals (**Table 1**). This translates to an estimated target population size of approximately 45,000 patients with qualifying nodules. Allowing for site-level variation in the proportion of patients with a prior history of cancer and patients with nodules detected on prior chest CT scans, we will passively enroll a minimum of 35,200 individuals with a nodule ≤ 15 mm at one of the 14 health systems (24 individual study sites for cluster randomization) during the initial 28-month recruitment period. To allow time to complete the evaluation and accrue outcomes, patients will be followed for at least 2 years during the funding period. Among these individuals with small pulmonary nodules, we assume (based on data from KPSC) that 3.0% will be diagnosed with lung cancer, resulting in a sample size of approximately 1,056 patients with cancerous nodules.

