We will continue recruitment through the end of the study to collect additional data for HTE analyses with greater statistical power for Aim 1. We assume 10% loss to follow-up before final diagnosis is established based on KPSC membership data. This yields an estimated sample size for analyses of 960 individuals with cancerous nodules for Aim 1, and 32,000 individuals with small nodules for Aims 2-4.

Aim 1: For the primary outcome, the baseline risk of progression has not been reported. Conservatively, we assume that 5% of patients will progress from a tumor ≤ 15 mm to a tumor > 20 mm during the surveillance period. Assuming a two-sided alpha of 0.05, and an intraclass correlation coefficient (ICC) of 0.01, a sample size of 888 unique patients with cancerous lung nodules (444 per arm) is required to achieve 83% power to detect an absolute increase in tumor progression of 5 percentage points. Thus, our anticipated sample size of 960 unique patients with cancerous lung nodules provides adequate power to show non-inferiority of the less intensive surveillance strategy for our primary outcome of lung cancer stage $> T1a$ at diagnosis. The most uncertainty in our assumptions is for the ICC. We will have at least 80% power to detect a 5% increase in our primary outcome for ICC values of 0.012 or less. At the baseline ICC value of 0.01, a total sample size of 32,560 enrolled (including 888 patients with cancerous nodules) will have 0.83 power; for an ICC value of 0.012, a total sample size of 35,200 enrolled (960 patients with cancer) will also have 0.83 power.

Aim 2: Prior studies of anxiety and distress in lung cancer screening have shown that the identification of a lung nodule leads to anxiety and emotional distress that subsequently dissipates over 1-2 years.^{56 63 52} For our analyses of anxiety and emotional distress, we will have $> 90\%$ power to detect an effect size of 0.22 standard deviation, assuming an ICC of 0.01, even if the response rate is as low as 5%, resulting in an estimated sample size of approximately 792 respondents in each arm.

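### The secondary time-to-event analyses rely on a site-clustered sandwich variance with 24 randomised clusters and no stated small-sample method, so their intervals can be too narrow

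*Combined protocol and SAP*

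**What the plan says.** In the Analysis Plan, the text under H1c sets one rule for every time-to-event analysis: Cox regression in which "clustering by site will be handled by specifying subjects nested within each cluster and using robust sandwich estimators for statistical inferences". This covers time to diagnosis, time to treatment and overall survival, all listed as secondary endpoints of Aim 1. No finite-sample correction, t reference, jackknife or permutation test is named there or elsewhere in the document.

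The number of clusters is small. The sample size section counts "24 individual study sites for cluster randomization", and the Abstract says "Eligible patients will be enrolled passively at one of 24 hospitals within 14 health care systems". The 24 arise because all but one of the 14 systems are randomised whole, and the exception is "KPSC, which operates hospitals in 11 distinct medical service areas (MSA"): 13 + 11 = 24. On allocation, the Cluster Randomization section states: "Random assignment to one of the two intervention groups at the hospital or health system level will be performed using matching", together with re-randomisation, on CT volume, setting type, smoking, insurance and other factors.

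The H1a text plans the primary model with and without the facility-level factors balanced at randomisation. The time-to-event text does not say whether the Cox models follow suit. It also does not define site. The sample size section counts 24 sites, but the Inclusion Criteria list of sites enrolling screen-detected nodules counts Kaiser Permanente Southern California as one.

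**The concern.** The cluster sandwich variance is justified when there are many clusters. Here the treatment contrast is between roughly 12 units per arm, however many patients each contributes. With so few units the ordinary estimator is biased downward, and a normal critical value ignores the uncertainty in the variance itself. Both push intervals to be too narrow.

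The stakes are highest for survival. H1c is a non-inferiority claim, and an interval that is too narrow there favours declaring less surveillance acceptable. For time to diagnosis, it would favour declaring a difference between arms.

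**Working it through.** **Inputs from the documents.** 24 randomised units; "our anticipated sample size of 960 unique patients with cancerous lung nodules", so 960/24 = 40 per unit; "Assuming a two-sided alpha of 0.05, and an intraclass correlation coefficient (ICC) of 0.01"; and, for the primary endpoint only, "Conservatively, we assume that 5% of patients will progress" with a 5-point margin. No power, event count or margin is given for any time-to-event endpoint.

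**Step 1: the plan's own figure.** Only the primary endpoint's power can be reproduced. It shows which cluster count the planning used.
- 888 cancers, 24 clusters: 37 per cluster; design effect 1 + 36 × 0.01 = 1.36; effective n per arm 444/1.36 = 326.5. SE = √(2 × 0.05 × 0.95/326.5) = 0.01706. Power = Φ(0.05/0.01706 − 1.96) = Φ(0.971) = 0.834, against 0.83 stated.
- 960 cancers, ICC 0.012: design effect 1 + 39 × 0.012 = 1.468; effective n 480/1.468 = 327.0; power 0.835, against 0.83 stated.
- 888 cancers, 14 clusters: design effect 1.624; effective n 273.4; power 0.765, which does not match.

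So the planning took the 24 randomised units as the clusters.

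**Step 2: approximate size of the effect.** With G equal clusters and k site-level covariates, the plain sandwich variance averages about (G − 2 − k)/G of the true variance and behaves like an estimate on G − 2 − k degrees of freedom. A nominal 5% z test then rejects with probability P(|t| > 1.96 × √((G − 2 − k)/G)), with t on G − 2 − k df.
- G = 24, k = 0: 1.96 × 0.957 = 1.877 on 22 df gives 7.4%.
- G = 24, k = 3 (assumed): 1.96 × 0.890 = 1.744 on 19 df gives 9.7%.
- G = 14, k = 0: 1.96 × 0.926 = 1.815 on 12 df gives 9.5%.

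**Step 3: simulated null Cox trials, plain sandwich with z.** There were 24 clusters, 12 per arm (split assumed), and about 960 cancers. Assumptions: log-normal site effect with variance 0 to 0.10, and coefficient of variation (CV) of cluster size 0 to 0.8. The two tables used 3,000 trials per setting (Monte Carlo error up to about 0.6 points).

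| Setting, matching ignored | Two-sided error |
|---|---|
| Equal sizes | 7.1-8.5% |
| Size CV 0.5 | 7.7-9.1% |
| Size CV 0.8 | 8.0-11.3% |
| 14 systems used as the clusters | 8.8-15.0% |

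One-sided error was 3.4-4.0% with equal sizes and about 5.5% at CV 0.8, against 2.5%.

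With pair-matched allocation and an unadjusted Cox model, site variance 0.02 or 0.10 and size CV 0 or 0.8:

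| Share of site variance captured by matching | Two-sided error |
|---|---|
| 25% | 5.0-8.4% |
| 50% | 2.9-6.5% |
| 75% | 0.9-4.5% |

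Other settings broadly agree. A set with 500 trials per setting gave 8-10% at 0-25% capture and 4.0-8.0% at 50%. Under pair matching with no site variance at all (1,200 trials per setting), the error was 8.0-8.1%. Adding three site-level factors gave 8.8-12.9%, even where matching captured 50-75% of the variance.

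**Step 4: the remedy.** A leave-one-site-out jackknife with t on 22 df gave 4.3%, 5.7% and 6.0% at size CV 0, 0.5 and 0.8 without matching (1,500 trials, site variance 0.02). In the 500-trial set, with 19 df when three factors were added, it gave 2.2-6.0%. In an unadjusted model after matching it was conservative: 1.3-3.4% at 50% capture and 0.7-2.9% at 75%.

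Interval widening, with a (G − 2 − k)/G variance correction and t: 2.074/1.877 = 1.105 for k = 0, and 2.093/1.744 = 1.200 for k = 3.

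**The case against.** The strongest reply is the allocation design. Matching and re-randomisation remove between-arm variance that an unmatched sandwich still counts, which offsets the downward bias. The second table in Step 3 shows that the offset can be complete. This stands, and a fixed jackknife with 22 df could then cost power. But the documents do not give the share captured. The offset also needs real site variance, and in the simulations it disappeared once site-level factors were in the model.

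A reader might infer that the plan commits to an uncorrected variance with a normal reference. It does not. The text is silent, which permits the plain version but does not require it.

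A reader might also infer that all these intervals will cover less than 95%. That is not supported, because the direction depends on the matching and on adjustment choices that the plan leaves open.

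Finally, these are secondary endpoints. The primary endpoint uses a logistic model with random site effects. The Aim 1 outcomes text already concedes limited follow-up for deaths, and no survival margin is given, so no changed conclusion can be shown.

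**Conclusion.** The point holds as a gap in specification that affects secondary endpoints only. With 24 clusters, an ordinary sandwich with z gives about 7-11% two-sided error instead of 5% when matching captures little of the site variance, and about 9-13% with three site-level factors. If the Cox model is unadjusted and matching captures about half or more, the error is near or below 5% in many settings, though up to 8.0% in some. These figures rest on assumed site variance, size variation, event rates, a 12:12 split and the number of factors. Unequal sizes are plausible: the Aim 3 outcomes text expects about 22,000 of the 35,200 patients at California sites. The actual error therefore depends on choices that the plan can still make in advance. It should make them.

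**What to change.** In the time-to-event paragraph under H1c:

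1. Define the cluster as the 24 randomised units (11 service areas and 13 systems).
2. State whether the Cox models adjust for the facility-level factors balanced at randomisation, and which.
3. Replace the plain sandwich with a bias-corrected or leave-one-site-out jackknife variance, and use a t reference for tests and intervals with df = 24 − 2 − the number of site-level covariates (22 if none, 19 with three). Alternatively, specify a permutation test that follows the matched, re-randomised allocation.

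The cost is SAP wording and a few lines of code, with no new data. Intervals become about 10% wider without site-level covariates and about 20% wider with three. The t-based option will be somewhat conservative if matching is strong and not adjusted for. The permutation test follows the design and avoids reliance on the df formula.

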The organizations were chosen for geographic, socioeconomic, and racial/ethnic diversity of patients; and for diversity in the size and type of health care delivery system: fee for service, capitated HMO, integrated, and academic. We plan to enroll approximately 35,200 participants with small nodules at these sites during a 28-month period, providing sufficient statistical power for the study aims. We will include consecutive patients with small nodules, so the assembled cohort will reflect the diversity of patients seen at all participating institutions. The large number

and types of facilities and highly diverse populations will provide results that are generalizable to the broader U.S. population.

Inclusion Criteria: The target population includes adults with small lung nodules, who typically would be managed by CT surveillance in usual clinical practice. Thus, we will enroll all adult patients aged ≥ 35 years with at least one newly identified nodule measuring ≤ 15 mm in average cross-sectional diameter on chest CT. We increased the original age threshold from 21 years to 35 years, because lung nodules and (especially) lung cancer are extremely rare in individuals younger than age 35, and the new Fleischner Society guidelines are specifically designed for individuals who are 35 years-old or older. The intention to treat population will include patients with nodules of this size who do or do not undergo surveillance imaging. We anticipate most patients will be >50 years old, as both CT use and nodule detection are more common in older patients. Further, because CT scanning is used more frequently in persons with chronic illness, we expect a high proportion of patients to have comorbidities. To accommodate the implementation of lung cancer screening in many settings, we will include individuals with nodules detected either incidentally or by screening at 6 participating sites: HealthPartners, Kaiser Permanente (Colorado, Northwest, Southern California), Medical University of South Carolina, and UC Davis.

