Anticipated Characteristics of the Study Population: In a preliminary study at one of our sites (KPSC), we reviewed chest CT results for approximately 240,000 health plan members who underwent imaging between 2006 and December 2012, and identified 68,998 patients with a pulmonary nodule ≤ 30 mm in size. Virtually all nodules during this time period were detected incidentally, because these data predated implementation of lung cancer screening with LDCT. The mean age was 63.6 ± 14.3 years; 55% were women; 48% were never smokers, 40% were former smokers and 11% were current smokers. The population was racially and ethnically diverse: 18% were Hispanic, 12% were non-Hispanic black, and 9% were Asian/Pacific Islander. Co-morbidities were frequent, including hypertension (58%), diabetes (22%), obstructive lung disease (14%), asthma (13%), coronary disease and/or heart failure (25%), and anxiety or depression (25%). Most (70%) nodules measured ≤ 15 mm. After excluding patients

with a prior history of cancer, 3% of patients with small nodules of this size were subsequently diagnosed with lung cancer within the next 2 years. We believe this sample is representative of patients with nodules identified in real-world settings and whom we will enroll and follow in the proposed trial. We anticipate having even greater patient diversity during the study because we will enroll participants from multiple geographic regions and from urban centers and safety net hospitals such as Boston Medical Center.

Research Design and Methodology

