H1a: Among participants with nodules that prove to be cancerous, less intensive surveillance will be non-inferior to more intensive surveillance for: (a) the frequency of cancer progression beyond AJCC 7th edition stage T1a disease (or T1b for AJCC 8th edition) and (b) the frequency of cancer progression beyond AJCC 7th edition TNM stage T1aN0M0 (or T1bN0M0 for AJCC 8th edition). In addition, among participants with *lung nodules*, less intensive surveillance will be non-inferior to more intensive surveillance for: (a) the frequency of cancer progression beyond AJCC 7th edition stage T1a disease (or T1b for AJCC 8th edition); and (b) the frequency of cancer progression beyond AJCC 7th edition TNM stage T1aN0M0 (or T1bN0M0 for AJCC 8th edition).. Furthermore, in exploratory analyses for HTE, we hypothesize that individuals who are most likely to benefit from more intensive surveillance will include older people, people with larger nodules (>8 mm), patients with solid or part-solid nodules (compared with non-solid

nodules), and individuals with nodules detected by screening (compared with individuals who have nodules that are incidentally detected).

H1b: Among participants with nodules that prove to be cancerous, more intensive surveillance will result in more timely diagnosis than less intensive surveillance.

H1c: Among participants with nodules that prove to be cancerous, less intensive surveillance will be non-inferior to more intensive surveillance for overall survival. Among participants with lung nodules, less intensive surveillance will be non-inferior to more intensive surveillance for overall survival.

H2a: Among all participants with a lung nodule ≤ 15 mm, more intensive surveillance will be associated with greater levels of emotional distress and state anxiety at 13-24 months, but levels of distress and anxiety similar to less intensive surveillance at 1-2 months and ≥ 25 months.

H2b: Among all participants with a lung nodule ≤ 15 mm, more intensive surveillance will be associated with scores similar to less intensive surveillance for general health status at 1-2 months, 13-24 months and ≥ 25 months.

H2c: Among participating radiologists and pulmonologists, satisfaction with the surveillance protocol will be greater among those who practice at institutions assigned to the less intensive protocol.

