Subgroup Analyses/Heterogeneity of Treatment Effect: During the 7.5-year study period, we will have sufficient power to achieve our primary aims based on the planned 28 months of enrollment. We limited the period of enrollment to enable follow-up of all enrolled patients for at least 2 years, to reliably exclude a diagnosis of cancer when absent, and to assess cancer outcomes when present. Analyses will include whether outcomes vary by CT indication (lung cancer screening or unrelated to lung cancer screening), lung cancer risk factors (primarily smoking history), nodule density (solid, part-solid or non-solid), health care setting, demographic characteristics, and geographic region. Each of these subgroup analyses will be guided by the clinically plausible, pre-specified hypothesis that more intensive surveillance is more effective in subgroups that are at higher risk for more aggressive forms of lung cancer, such as older individuals; smokers and former smokers; patients with screening-detected nodules, solid nodules, or nodules of larger size; and patients from regions where a large portion of nodules are caused by endemic fungal infections.

To examine differences in “treatment” effect, we will include relevant interaction terms in all regression models, and report magnitudes of effects and standard errors for each subgroup level when interactions are statistically significant.

[figure not shown]
Missing Data: Two types of missing data might occur: (1) core study variables (such as potential confounders) may be missing for some patients because of incomplete capture in the

EHR, and (2) patients might disenroll from a health system and/or leave the capture area. We will minimize missingness of core study variables through intensive quality assurance. The Data Coordinating Center will review monthly reports for potential data issues and follow-up with site coordinators and programmers to abstract missing data, correct data issues, and document in the study database when missing data cannot be found.

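### The exploratory treatment-by-age interaction appears to be tested on median and/or quartile age groups; a single prespecified test on continuous age would use the data better at almost no cost

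*Combined protocol and SAP*

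**What the plan says.** All references are to the combined protocol and SAP.

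- **Hypotheses, H1a.** In exploratory analyses of heterogeneity of treatment effect (HTE), the plan expects that "individuals who are most likely to benefit from more intensive surveillance will include older people". The section Subgroup Analyses/Heterogeneity of Treatment Effect repeats the direction for age. Neither place names a threshold age.
- **Analysis Plan, subgroup text under H1c.** Age is to be examined "using the median and/or quartile values as cut points", alongside nodule size, attenuation and mode of detection. The plan continues: "we will include interaction terms between each of these factors with treatment in the models, respectively". Significant interactions are followed by analyses within the corresponding subgroups.
- **Same paragraph, on status.** "Since the study is not powered to test interaction terms, these analyses will be exploratory".
- **Subgroup Analyses/Heterogeneity of Treatment Effect, on reporting.** The investigators will "report magnitudes of effects and standard errors for each subgroup level when interactions are statistically significant".

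Age is also listed as an adjustment covariate for the primary model, without a stated form. No section gives a continuous form for age in the interaction.

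**The concern.** The factors that receive interaction terms are those just listed, and age has just been described as cut into groups. Read naturally, the interaction test therefore uses grouped age.

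Three features of the plan make this a poor fit:

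1. The hypothesis has a direction but no threshold. A median split tests for a step at the sample median and ignores age differences within each half.
2. Subgroup effects are explored or reported only when the interaction is significant. A less sensitive test makes it more likely that a real age gradient is never shown. The sample size section also says recruitment continues partly to gain power for HTE in Aim 1, and grouping gives some of that back.
3. Research Design and Methodology undertakes to specify HTE analyses in advance. The and/or wording does not settle whether there are two or four groups, whether quartiles enter as a trend or as a 3-df factor, or whether the cut points come from all enrolled patients or only those with cancer.

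What is at stake is the sensitivity and clarity of one exploratory test.

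**Working it through.** **Step 1. The plan's own power figure.** The plan gives no power for any interaction. Its nearest figure is for the primary outcome under Sample size and power calculations, Aim 1: "Assuming a two-sided alpha of 0.05, and an intraclass correlation coefficient (ICC) of 0.01, a sample size of 888 unique patients" with cancer, 444 per arm, for 83% power. The other inputs are 5% baseline risk, a 5-point margin and 24 randomised sites.

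- Patients per cluster: 888/24 = 37. Design effect: 1 + 36 × 0.01 = 1.36.
- Effective number per arm: 444/1.36 = 326.5.
- Standard error: √(2 × 0.05 × 0.95/326.5) = 0.0171.
- Power: Φ(0.05/0.0171 − 1.96) ≈ 0.83.

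The stated figure is reproduced, and nothing in it depends on how age is coded.

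**Step 2. Information kept by grouping.** If the treatment effect changes linearly with age, the share of information kept is the variance of the group mean ages divided by the total variance of age. The only age summary in the documents is from the preliminary cohort (Anticipated Characteristics of the Study Population): "The mean age was 63.6 ± 14.3 years". Under Inclusion Criteria, "we will enroll all adult patients aged ≥ 35 years".

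Median split, normal age:
- The half means lie 14.3 × √(2/π) = 11.4 years either side of 63.6, at 52.2 and 75.0.
- Share kept: 11.4²/14.3² = 2/π = 0.637. Loss: 36.3%.
- For 960 cancers this is like testing in 960 × 0.637 = 611. Equal power would need 1/0.637 = 1.57 times the sample.

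Quartile groups, normal age:
- The group means are 45.4, 59.0, 68.2 and 81.8.
- Share kept: 0.861, a loss of 13.9%. An equally spaced quartile score keeps 0.856.

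**Step 3. Sensitivity to the age distribution.**

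| Assumed age distribution | Loss, median split | Loss, quartile groups |
|---|---|---|
| Normal (63.6, 14.3) | 36.3% | 13.9% |
| Same, cut off below 35 | 34.7% | 12.4% |
| Same, restricted to 35–95 | 33.0% | 10.7% |
| Uniform, 35–90 | 25% | 6.3% |
| Heavy-tailed (Laplace) | 50% | 26% |

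The first three rows use the documents' mean and SD; the upper limit of 95 is an assumption. The last two rows only show how far the shape matters.

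**Step 4. What this means for power.** Suppose, purely for illustration, that a linear interaction had 80% power with continuous age (two-sided 0.05, noncentrality 7.85). With normal age:

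- Median split: 7.85 × 0.637 = 5.00, power 61%.
- Quartile trend score, 1 df: 7.85 × 0.856 = 6.72, power 74%.
- Quartiles as a factor, 3 df: 7.85 × 0.861 = 6.76, power 57%. Here the extra degrees of freedom cost more than the finer grouping gains.

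**Step 5. Events available for a non-linearity check.** At the assumed 5% progression, 960 cancers give 960 × 0.05 = 48 primary events. If both arms reached 10%, there would be 96. A spline-by-treatment term on so few events can detect little.

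**The case against.** The strongest reply is that little depends on this. The age hypothesis is placed among exploratory analyses, the plan admits that interactions are not powered, and no primary or secondary conclusion rests on the test. That stands, and it limits the point to a minor improvement.

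The text also never says outright that age is categorical in the interaction model. The cut points could be meant only for the follow-up subgroups, which would come close to the fix below. This reading is possible but less natural, and the ambiguity is itself worth a sentence.

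A reader might infer several stronger things that the documents do not support:

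- **That the cut age can be searched for a favourable result.** The median and quartiles follow from the age distribution, not from outcomes. Only the number of groups and the reference population are open.
- **That the analyst will choose a grouping after seeing results.** The wording permits this but does not describe it, and may simply mean that both groupings are reported. If significance were declared when either the median test or the 3-df quartile test reached 0.05, simulation gives about 8.1% false positives, but the plan states no such rule.
- **That the hypothesis is a linear trend, so grouping has no merit.** The plan states only a direction. If the effect really changed at a threshold, grouping would lose less, and groups do not impose linearity. No section proposes such a threshold, however.

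**Conclusion.** The point holds as a free improvement to an exploratory analysis. On the natural reading, age is grouped before its interaction with treatment is tested, and the number of groups and the reference population are not fixed.

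With a roughly linear interaction and roughly normal age, the loss is about 33–36% for a median split. For quartile groups it is about 12–14%, or about 11% with ages also capped at 95. These figures borrow the mean and SD of a preliminary cohort with nodules up to 30 mm; age among the trial's cancers is not given.

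The 36% should not be read as a fixed or maximum loss. It belongs to one combination (median split, normal age, linear interaction), and other distributions give less or more. The primary result, the non-inferiority margin and the sample size are unaffected.

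**What to change.** Amend the subgroup text under H1c, and cross-refer to it from the HTE section, so that:

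1. Treatment by continuous age, entered linearly, is the single prespecified age interaction test.
2. The treatment effect is reported with its confidence interval at a few ages fixed in advance.
3. One age grouping, with its number of groups and reference population stated, is used for display only.

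A restricted cubic spline may be added as a check, with a note that it has little ability to detect non-linearity for the primary endpoint given the 48 to 96 events worked out above.

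The cost is a sentence or two in the SAP and no new data. The small downside is that a linear term assumes a smooth trend and would describe a true threshold less well. If results have already been seen, the continuous analysis should be added as a labelled supplementary analysis, with a statement of which grouping was used.
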